10.1.2 Serious Adverse Events (SAEs)

Each AE must be classified by the investigator as SERIOUS or NONSERIOUS. An AE that meets 1 or more of the following criteria (or outcomes) is classified as serious:

- Death
- Life-threatening (see paragraph below on Life-threatening)
- In-patient hospitalization or prolongation of existing hospitalization (see paragraph below on Hospitalization)
- Persistent or significant disability or incapacity (see paragraph below on Disability)
- Congenital anomaly or birth defect
- Is considered a medically important event not meeting the above criteria, but which may jeopardize a subject, or may require medical or surgical intervention to prevent one of the criteria listed in this definition.

Serious also includes any other event that the investigator or sponsor judges to be serious. If there is any doubt whether the information constitutes an AE or SAE, the information is to be treated as an SAE.

Life-threatening – Any event in which the subject was at risk of death at the time of the event; 'life-threatening' does not refer to an event which hypothetically might have caused death if it were more severe. For example, drug-induced hepatitis that resolved without evidence of hepatic failure would not be considered life threatening, even though drug-induced hepatitis of a more severe nature can be fatal.

Hospitalization – Hospitalization is defined as an overnight admission with observation of a minimum of 24 hours. A hospitalization planned before the start of the study for a pre-existing condition that has not worsened during the AE reporting period does not constitute an SAE unless an untoward event occurs related to the procedure (eg, elective hospitalization for a total knee replacement due to a preexisting condition of osteoarthritis of the knee that has not worsened during the study).

Disability – Defined as a substantial disruption in a person's ability to conduct normal life functions.

10.2 Eliciting Adverse Event Information

The investigator is to report all directly observed AEs and all AEs spontaneously reported by the study subject. In addition, each study subject will be questioned about AEs at each visit following the initiation of treatment.

10.3 Reporting

Each AE is to be classified by the investigator as SERIOUS or NONSERIOUS.

All AEs that occur in study subjects during the AE reporting period specified in the protocol must be reported whether or not the event is considered related to study medication.

10.3.1 Reporting Period

The AE reporting period for a subject begins upon receiving the first dose of study medication and ends at the final protocol-required visit.

In addition, SAEs that occur after the protocol-defined AE reporting period that are considered to be related to the study medication should be recorded and reported to the sponsor's medical monitor or CRO designee.

10.3.2 Reporting AEs

NONSERIOUS AEs are to be reported on the AE CRF.

10.3.3 Reporting SAEs

Any SAE, regardless of causal relationship, must be reported to the sponsor's medical monitor (or medical director) or CRO designee within 24 hours after the investigator becomes aware of the SAE. Compliance with this time requirement is essential so that the sponsor may comply with its regulatory obligations.

The initial SAE report should be completed as fully as possible but should contain, at a minimum:

- Subject identification number, sex, age, and date of birth
- Date of report

- Name of the reporter
- Name of the suspected medicinal product
- Description of the event, including event term(s), seriousness criteria, and a clinical summary of the event
- Causality assessment

Information about all SAEs (either initial or follow-up information) should be collected and recorded in English on the electronic SAE Report Form within the electronic data capture (EDC) system. The investigator must assess the relationship to each specific component of the study treatment. If the event meets serious criteria and it is not possible to access the EDC system, a paper SAE Report Form should be sent to the CRO via email or fax within 24 hours of being made aware of the SAE (reference the site manual for contact information). When the EDC system becomes available, the SAE information must be entered within 24 hours of the system becoming available.

The investigator must report follow-up information relating to an SAE to the sponsor's medical monitor (or medical director) or CRO designee within 24 hours of awareness by updating the electronic CRF with the new information or by submitting a paper SAE Report Form (only if the EDC is not available). When the EDC system becomes available, the SAE information must be entered within 24 hours. The subject should be observed and monitored carefully until the condition resolves or stabilizes.

All deaths are to be thoroughly investigated and reported. Autopsy reports are to be obtained, if possible, and sent to the CRO via email or fax.

The sponsor or its designee are responsible for reporting SAEs to all applicable regulatory agencies and the central ethics committees within the required timeline.

The investigators are responsible for submitting required safety information to their local IRB per local regulations. This information includes but is not limited to, any safety alert letter received from the sponsor and any SAEs occurring at their investigative site.

10.3.4 Relationship to Study Medication

The causal relationship of the AE to study medication will be assessed by both the investigator and the sponsor. The investigator should provide causality assessment with the initial SAE report within 24 hours of becoming aware of the event.

The assessment of causal relationship to study drug should be evidence-based, and not based on the premise that all AEs are possibly causally related to study drug until proven otherwise.

Examples of evidence that would suggest a causal relationship between the drug and the AE include the occurrence of an AE that is uncommon and known to be strongly associated with drug exposure (eg, angioedema, hepatic injury, Stevens-Johnson Syndrome), or an AE that is uncommon in the population exposed to the drug.

The causal relationship of the AE is assessed using a binary system, and AEs are classified as either 'related' or 'unrelated':

Related: There is 'reasonable possibility' that the drug caused the AE. The AE follows a reasonable temporal sequence from the time of drug administration. There is supportive evidence

(facts) to suggest a possible causal relationship, irrespective of the degree of certainty between the observed AE and the drug.

Unrelated: An AE does not follow a reasonable temporal sequence from administration of the product and/or there is no reasonable possibility that the drug caused the AE. This assessment includes situations where the AE is related to other factors such as the subject's clinical state, other therapeutic interventions, or concomitant drugs administered to the subject.

Default assessments using the 'related' category without supportive evidence for a causal relationship to study drug is generally uninformative and does not contribute meaningfully to the development of the safety profile of the drug or to subject protection.

Investigators are encouraged to choose the most plausible cause for the event(s) from the following list: medical history, lack of efficacy or worsening of treated condition, study treatment, other treatment (concomitant, or previous), withdrawal of study treatment, administration error, protocol-related procedure, others (specify).

10.3.5 Severity

The investigator will assess each AE as either MILD, MODERATE, or SEVERE using the following guidelines to describe the maximum severity of the AE:

- MILD: Does not interfere with subject's usual function.
- MODERATE: Interferes to some extent with subject's usual function
- SEVERE: Interferes significantly with subject's usual function.

Note that a **severe** AE is not necessarily a **serious** AE. For example, a headache may be severe in intensity, but would not be classified as serious unless it met 1 of the criteria for serious events listed above.

10.3.6 Follow-Up of Unresolved Events

All AEs should be followed until they are resolved or the investigator assesses them as chronic or stable or the subject's participation in the study ends (ie, until a final report is completed for that subject).

In addition, all SAEs and those non-serious events assessed by the investigator as related to the study medication should continue to be followed even after the subject's participation in the study is over. Such events should be followed until they resolve or until the investigator assesses them as "chronic" or "stable." Resolution of such events is to be documented on the appropriate CRF.

10.4 Exposure In Utero

A pregnancy in a female subject must be confirmed by a positive serum β human chorionic gonadotropin (β -HCG) test.

The study medication should be immediately discontinued once the pregnancy of a female subject has been confirmed.

If any study participant becomes or is found to be pregnant while receiving a study medication or within 30 days of discontinuing the study medication, the pregnancy must be recorded on the Pregnancy Reporting Form/Exposure In Utero Form within 24 hours of awareness of the

pregnancy and sent to the CRO via email or fax (reference the site manual for contact information).

Pregnancy during this time frame of the female partner of a male subject should also be reported.

The Pregnancy Reporting Form/Exposure in utero Form must be completed with all known information regarding the pregnancy at the time of reporting. Investigative site personnel will update the form with additional information regarding the pregnancy and the outcome of the pregnancy as it becomes available until the outcome of the pregnancy is reported.

The investigator will follow the subject (or female partner of a male subject) until completion of the pregnancy. If the outcome of the pregnancy meets the criteria for immediate classification as an SAE (ie, spontaneous abortion, stillbirth, neonatal death within 1 month of birth, or congenital anomaly [including that in an aborted fetus]), the investigator should follow the procedures for reporting an SAE within 24 hours of awareness. A pregnancy in and of itself is not considered an AE; however, unexpected complications are considered AEs.

Additional information about pregnancy outcomes follows:

- Note that "spontaneous abortion" includes miscarriage and missed abortion.
- Neonates should be followed through gestational age of 46 weeks.
- Follow-up information includes the course, duration, and the outcome of the pregnancy and the neonate's health.
- All neonatal deaths that occur within 1 month of birth should be reported, without regard to causality, as SAEs. In addition, any infant death after 1 month that the investigator assesses as related or unrelated to the in utero exposure to the study medication should also be reported.
- In the case of a live birth, the "normality" of the newborn can be assessed at time of birth.
- The "normality" of an aborted fetus can be assessed by gross visual inspection unless there are pre-abortion laboratory findings suggestive of a congenital anomaly.

10.5 Special Situations

Certain safety events, called 'Special Situations', that occur in association with study drug(s) may require reporting. These Special Situations include, but are not limited to, the following:

- Overdose of the study drug
- Suspected abuse or misuse of the study drug
- Inadvertent or accidental exposure to the study drug
- Medication error involving the study drug (with or without subject exposure to the sponsor's study drug, eg, name confusion)
- Drug-drug interaction involving the study drug

Special situations should be reported on the Special Situations CRF whether they result in an AE/SAE or not. Special situations with associated AE/SAE should also be reported on the corresponding AE/SAE forms, following applicable AE or SAE process.

11 DATA ANALYSIS

Data collected throughout the study will be summarized using descriptive statistics and listed in by-subject listings. Continuous variables will be summarized using number of subjects with data, mean, standard deviation, median, minimum, and maximum. For categorical variables, the number and percentage of subjects in each category will be tabulated.

For continuous endpoints (eg, Hb) where change from baseline will be analyzed and multiple pretreatment values are recorded, baseline will be defined as the mean of all qualifying values collected prior to the first dose of study drug. For other continuous endpoints baseline will be defined as the last available value prior to the first dose of study drug.

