5.2 Secondary Objectives and Endpoints

The secondary objectives of this study are to evaluate the safety and efficacy of vadadustat compared to epoetin alfa in subjects with anemia secondary to DD-CKD who are hyporesponsive to ESAs.

Secondary endpoints:

- Proportion of subjects demonstrating incremental increases in Hb from baseline over time during the treatment period
- Proportion of subjects with Hb values within the target range of 10.0-11.0 g/dL during the treatment period
- Proportion of subjects receiving epoetin alfa rescue
- Proportion of subjects receiving RBC transfusion
- Levels of various biomarkers, including CRP, hepcidin, and vascular endothelial growth factor (VEGF)
- Mean weekly dose of intravenous elemental iron
- Maintenance of iron sufficiency (defined as ferritin ≥100 ng/mL and transferrin saturation [TSAT] ≥20%).
- Resource utilization

Safety endpoints in this study include the following:

- Hb >12.0 g/dL, >13.0 g/dL, or >14.0 g/dL
- Hb increase >1.0 g/dL within any 2-week interval or >2.0 g/dL within any 4-week interval
- AEs and SAEs
- Vital sign measurements and clinical laboratory values

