7.2 Inclusion Criteria

Subjects must meet all the following inclusion criteria to be eligible for study participation:

- 1. ≥ 18 years of age
- 2. Receiving chronic maintenance in-center hemodialysis (3 times per week) for end-stage renal disease for at least 6 months prior to screening
- 3. Currently receiving epoetin alfa for anemia
- 4. Two Hb measurements (by central lab analysis) between 8.5 and 10 g/dL during screening
- 5. Administered intravenous supplemental iron per investigative site's protocol to maintain serum ferritin \geq 100 ng/mL and TSAT \geq 20%
- 6. Folate and vitamin B12 measurements \geq lower limit of normal during screening
- 7. Having dialysis adequacy as indicated by k- dialyzer clearance of urea, t- dialysis time, V-volume of distribution of urea (Kt/V) >1.2
- 8. Understands the procedures and requirements of the study, willing and able to comply with all study procedures, and provides written informed consent and authorization for protected health information disclosure

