7.4 Retesting and Rescreening

7.4.1 Retesting

Retesting is defined as repeating laboratory tests within the same Screening Period.

All screening laboratory tests, including any repeat measurements, must be performed within the 28-day screening window with a minimum of 4 days between the last qualifying repeat measurement and the baseline visit on Day 1 (see Section 9.1).

Subjects who initially fail to qualify for the study based on laboratory test results may have their laboratory value retested once for each laboratory parameter within the 28-day screening period, at the investigator's discretion.

Retesting within the screening period does not constitute rescreening; however, if retesting falls outside of the screening period, it should be considered a rescreen (see Section 7.4.2).

For eligibility purposes, if Hb at screening visit 1 (SV1) is 10.0 to 10.5 g/dL, 1 retest complete blood count (CBC) should be performed prior to SV2. If the retest Hb is \geq 10.0 g/dL, the subject should not proceed with SV2. If the Hb at SV1 is >10.5 g/dL, the subject should not proceed with any further screening procedures at that time.

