9.2.5 Randomization

Subjects who meet all inclusion and none of the exclusion criteria will be randomly allocated (1:1 ratio) using the IWR system to participate in either the vadadustat or epoetin alfa treatment arm. Permuted block randomization will be used to assign subjects to treatment.

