9.4.2 Baseline Visit (Day 1)

There must be a minimum of 4 days between the last screening visit and the baseline visit.

On Day 1, blood sample collection and other baseline procedures should be completed prior to dosing with study drug (vadadustat or epoetin alfa). On Day 1, study drug will be administered at the investigative site, and may be administered prior to or during the dialysis session.

At the baseline visit, the following activities/procedures will be performed:

- Review of study inclusion and exclusion criteria
- Review acceptable methods of contraception
- Subject randomization
- Dry weight and dialysis treatment review
- Dialysis adequacy (from dialysis performed during screening)
- Vital signs
- 12-lead ECG (ECGs should be completed prior to blood draws when possible and should be obtained after the subject has been resting supine comfortably for approximately 10 minutes; ECG may be completed and reviewed by the investigator on Day 1 or if needed for scheduling reasons [eg, dialysis treatment is scheduled for early morning of Day 1], the ECG can be completed and reviewed up to 1-3 days prior to Day 1)
- AE review
- Recording of any concomitant medication use since screening visit
- Laboratory procedures (if blood samples are collected on a day of dialysis, blood draws should be done prior to dialysis, if applicable):
 - Urine pregnancy test (see Section 9.3.2 for additional information)
 - CBC with differential
 - Reticulocyte count
 - Coagulation tests
 - C-reactive protein
 - Serum chemistry
 - Liver function tests

- Iron indices
- Lipid panel
- Sample for PK analysis (vadadustat treatment arm only; the sample will be collected between 30 minutes to 1 hour after vadadustat administration either prior to or during dialysis; the time of the vadadustat dose, the PK sample collection time, and the start and stop times of the dialysis session will be documented)
- Biomarkers
- o Sample for erythropoietin measurement
- Sample for exploratory analyses
- Subjects in epoetin alfa treatment arm will continue to receive epoetin alfa
- For subjects in the vadadustat treatment arm only:
 - Initiate vadadustat dosing
 - Vadadustat drug dispensation
 - o Review vadadustat dosing instructions
- Review use of rescue therapy (RBC transfusions and epoetin alfa rescue therapy)
- Review use of iron supplementation

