11.6 Efficacy Analyses

This study is exploratory in nature, designed to evaluate the change in Hb from baseline over time during the treatment period. No formal statistical testing will be performed.

Summary statistics (mean, median, standard deviation [SD], range, proportion and 95% confidence intervals when appropriate) will be provided, by treatment groups for primary and secondary endpoints.

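### Section 11.6 plans no between-arm estimate for the objective of comparing vadadustat with epoetin alfa

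*Combined protocol and SAP*

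**What the plan says.** - **Objectives.** Section 5.1 states the primary objective for vadadustat alone, with Hb change from baseline over time as the endpoint. Section 5.2 adds a comparative objective: to "evaluate the safety and efficacy of vadadustat compared to epoetin alfa".
- **Design.** Section 9.2.5 has subjects "randomly allocated (1:1 ratio) using the IWR system to participate in either the vadadustat or epoetin alfa treatment arm". Under Section 8.3.5 the vadadustat arm stops epoetin alfa when vadadustat starts. Under Section 8.3.4 the control arm continues its screening dose, with titration.
- **Efficacy analysis.** Section 11.6 calls the study exploratory and rules out formal testing. Summary statistics, with 95% confidence intervals where appropriate, "will be provided, by treatment groups for primary and secondary endpoints". Section 11.2 says efficacy analyses use both the MITT and the per-protocol populations. Section 11.5 bases the primary analysis on observed data without imputation and does not mention rescue.
- **Baseline.** For Hb, Section 11 says "baseline will be defined as the mean of all qualifying values collected prior to the first dose of study drug". The nearest use of the same word is in Section 7.4.1, which requires "a minimum of 4 days between the last qualifying repeat measurement and the baseline visit on Day 1". Entry needs "Two Hb measurements (by central lab analysis) between 8.5 and 10 g/dL during screening" (Section 7.2), and a further rule applies: "if Hb at screening visit 1 (SV1) is 10.0 to 10.5 g/dL, 1 retest complete blood count (CBC) should be performed prior to SV2". Section 9.4.2 adds a blood count on Day 1: "On Day 1, blood sample collection and other baseline procedures should be completed prior to dosing with study drug". Section 7.4.2 allows up to three screening attempts.

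**The concern.** Followed as written, the plan ends with two columns of summaries and no estimate for its comparative objective. Change within the vadadustat arm mixes starting vadadustat with withdrawing epoetin, and it has no control for time trend or for selection on screening Hb. The epoetin arm is there to supply that control, but nothing in Section 11 uses it.

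A reader could subtract one arm mean from the other. That figure would then be chosen after the data are seen, from any of ten post-baseline visits (Weeks 2 to 20) and either of two populations.

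The choice of population matters. The per-protocol set requires an epoetin dose recorded in Weeks 18 to 20 and no rescue in Weeks 12 to 20. Both conditions arise after randomization, and the first bears very differently on an arm that stopped epoetin on Day 1.

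The baseline wording is a smaller matter. Baseline might be the in-range screening values only, those plus Day 1, or every pre-dose value including a first-visit result that led to a retest. Values used to select subjects can carry regression to the mean into within-arm change.

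**Working it through.** **1. What can be reproduced.** Section 11.1 gives 2 x 25 = 50 subjects and no SD, effect size, alpha or power. There is no precision figure to reproduce, so the SDs below are assumptions.

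**2. Precision at 25 per arm.** The one-arm 95% half-width is t(24) x SD / sqrt(25), with t(24) = 2.064. The between-arm half-width is t(48) x SD x sqrt(2/25), with t(48) = 2.011 and sqrt(2/25) = 0.2828.

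| Assumed SD of change (g/dL) | One arm | Between arms, unadjusted |
|---|---|---|
| 0.7 | 0.29 | 0.40 |
| 1.0 | 0.41 | 0.57 |
| 1.2 | 0.50 | 0.68 |
| 1.5 | 0.62 | 0.85 |

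At SD 1.0: 2.064 x 1.0 / 5 = 0.413, and 2.011 x 1.0 x 0.2828 = 0.569.

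**3. Size of the baseline effect.** Screening was simulated with true Hb normal plus measurement error. Assumptions: between-subject SD 0.8 to 1.0, within-subject SD 0.4 to 0.6, uncorrelated errors, stable true Hb and one screening attempt. The 8.5 to 10 g/dL window and the first-visit retest rule were applied. The entries are the expected within-arm change (g/dL) when nothing truly changes.

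| Assumed source mean (g/dL) | In-range screening values | Plus Day 1 | All pre-dose values |
|---|---|---|---|
| 9.0 | -0.03 to 0.00 | -0.02 to 0.00 | -0.04 to -0.01 |
| 9.25 | +0.01 to +0.02 | +0.01 to +0.02 | -0.01 to 0.00 |
| 9.5 | +0.03 to +0.07 | +0.02 to +0.05 | +0.01 to +0.03 |
| 10.0 | +0.07 to +0.17 | +0.05 to +0.11 | +0.03 to +0.09 |
| 10.5 | +0.10 to +0.26 | +0.07 to +0.18 | +0.05 to +0.15 |

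Day 1 alone gives about 0. Section 7.4.1 also lets any failing laboratory value be retested once. Adding that rule moves the first column at means 9.0 to 9.5 to about -0.08 to +0.05 and changes it little at 10.0 and above. Together the two versions give -0.08 to +0.07. The three readings differ from one another by at most 0.05 g/dL at means 9.0 to 9.5, 0.08 at 10.0 and 0.11 at 10.5.

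**4. What the contrast does to it.** Randomization gives the selection effect the same expectation in both arms. In 3,000 simulated trials of 25 per arm in each of ten settings (source means 9.0, 9.5 and 10.5, no arm effect, no dropout), the average one-arm change ran from -0.04 to +0.26 across the three readings. The average between-arm difference stayed within about 0.01 of zero, adjusted or not. Within a single trial the difference still moved by 0.04 to 0.06 g/dL on average across the readings, so baseline should be fixed in advance as well.

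**5. Value of adjustment.** In one setting (mean 9.5, SDs 0.8 and 0.6) with a screening-only baseline, the half-width was 0.462 unadjusted and 0.466 by ANCOVA. With Day 1 alone as baseline it narrowed from 0.532 to 0.462.

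**The case against.** The strongest reply is that the omission is deliberate. The primary objective concerns vadadustat alone, Section 11.6 declares an exploratory study without testing, and Appendix B records that the objectives became exploratory and the analysis descriptive. Side-by-side summaries are a permissible descriptive answer, and no stated inference depends on a difference. This stands as a limit on severity. It does not remove the gap: Section 5.2 still asks for a comparison, the plan already uses confidence intervals, and an interval for a difference is estimation and not a test.

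A reader might infer that regression to the mean inflates the vadadustat result. The documents do not support that. They give no source mean or SD, the sign is unknown, and at assumed means up to 9.5 the effect is well inside the one-arm half-width. Values above 0.1 g/dL need a source mean of about 10.0 or more. Appendix B describes patients who could not hold Hb at 10.0 to 11.0 g/dL on high epoetin doses. That makes a mean as high as 10.5 hard to defend, though it does not fix the mean.

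Two further cautions stand. Covariate adjustment is a reasonable choice here but gains little precision. Cancellation between arms also assumes that missing data do not differ by arm. Under Section 7.6.2.2, subjects who stop study drug permanently go to end-of-treatment assessments and then Week 24, so later treatment visits may be missing unevenly.

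**Conclusion.** The gap is real and should be fixed: a stated comparative objective has no planned between-arm estimate, time point or population. No figure in the plan is shown to be wrong, and the primary endpoint and exploratory status can stay as they are.

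The added difference would estimate switching to vadadustat versus continuing epoetin. A reader might take it as the effect of vadadustat apart from epoetin withdrawal, but the design cannot separate the two.

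The undefined baseline term is a minor clarification, worth roughly -0.08 to +0.07 g/dL at assumed source means of 9.0 to 9.5 and more only at 10.0 or above. The half-widths rest on assumed SDs and complete data. The baseline figures rest on stable true Hb, uncorrelated errors and a single screening attempt.

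**What to change.** **Section 11.6.** Keep the by-arm summaries and the primary endpoint, and add the following:

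- The vadadustat-minus-epoetin difference in mean Hb change from baseline, with a 95% confidence interval, at one time point or window named in advance. Other visits are supportive. If Week 20 is chosen, state whether an early end-of-treatment value counts as Week 20.
- The MITT population, because the per-protocol set conditions on rescue and on epoetin dose records after randomization.
- A baseline-adjusted model on observed values: ANCOVA, or a repeated-measures model over the scheduled visits.
- An express statement that values after rescue are included, since Section 11.5 is silent, with the numbers of subjects with data and the numbers rescued shown per arm.
- A label: exploratory estimation without a test, read as switching to vadadustat versus continuing epoetin.

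**Section 11.** List which pre-dose central-laboratory Hb values form baseline. State whether Day 1, a first-visit value that led to a retest, other retests and values from earlier screening attempts count.

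**Cost.** Analysis wording only; all the values are already collected. The between-arm interval is wider than the one-arm interval (about 0.57 against 0.41 g/dL at SD 1.0). Adjustment adds little precision. The Hb target common to both arms, and rescue, can shrink the difference. Missing data that differ by arm could still bias it.
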